# **Exploratory Endpoints:**

- Immunogenicity of ETBX-021 by flow cytometric analysis of T-cell frequency, activation status, cytokine profiles, and antibody levels.
- Genetic and proteomic profiling and correlations with efficacy.

# Study Design:

This is a phase 1 trial in subjects with unresectable locally advanced or metastatic HER2-expressing (IHC 1+, 2+, or 3+) cancer. The study will be conducted in two parts: the first part will involve dose escalation using a 3 + 3 design, and the second part will involve the expansion of the MTD or HTD to further evaluate safety, preliminary efficacy, and immunogenicity. In the first part, 3 to 6 subjects will be sequentially enrolled starting at dose cohort 1. Subjects will be assessed for dose-limiting toxicities (DLTs).

- Cohort 1:  $5 \times 10^{10}$  virus particles (VP).
- Cohort 2:  $5 \times 10^{11}$  VP.
- If needed, dose de-escalation cohort (cohort -1):  $5 \times 10^9$  VP.

Dose expansion will occur when the MTD or HTD has been determined. An additional 12 subjects will be enrolled in the dose expansion component of the trial, for a total of 18 subjects at the MTD or HTD.

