# Enrollment (planned):

Up to 30 subjects will be enrolled in the study. In the dose escalation component, 3 to 6 subjects will be sequentially enrolled starting at cohort 1. In the dose expansion component (ie, once the MTD or HTD has been identified), an additional 12 subjects will be enrolled for a total of 18 subjects in the MTD/HTD cohort to obtain further safety, preliminary efficacy, and immunogenicity data.

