#### **Statistical Methods:**

The rate of DLTs and the MTD or HTD will be assessed. Overall safety will be assessed by descriptive analyses using tabulated frequencies of AEs by grade using CTCAE Version 4.03 within dose cohorts and for the overall study population in terms of treatment-emergent AEs, SAEs, and clinically significant changes in safety laboratory tests, physical examinations, ECGs, LVEF, and vital signs. ORR and DCR will be evaluated according to RECIST Version 1.1 by dose cohort and overall; duration of response will also be evaluated. PFS and OS will be analyzed using Kaplan-Meier methods by dose cohort and overall.

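### Does the stated total of 18 subjects at the MTD/HTD conflict with escalation cohorts of 3 to 6 subjects?

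*Combined protocol and SAP*

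**What the plan says.** The passages are in the combined protocol and SAP, Protocol Synopsis, Amendment 4.

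- **Study Design** sets out the escalation: "the first part will involve dose escalation using a 3 + 3 design", and "In the first part, 3 to 6 subjects will be sequentially enrolled starting at dose cohort 1". There are two planned dose cohorts and a de-escalation cohort to be used if needed.
- **Study Design** gives the trigger for expansion: "Dose expansion will occur when the MTD or HTD has been determined". No minimum number treated at that dose is attached to the trigger. The size of the cohort at the selected dose follows: "An additional 12 subjects will be enrolled in the dose expansion component of the trial, for a total of 18 subjects".
- **Enrollment (planned)** repeats the size: "an additional 12 subjects will be enrolled for a total of 18 subjects in the MTD/HTD cohort". It sets the overall ceiling: "Up to 30 subjects will be enrolled in the study".
- **Statistical Methods** describes the use of the data: "Overall safety will be assessed by descriptive analyses using tabulated frequencies of AEs by grade using CTCAE Version 4.03 within dose cohorts". The tumor endpoints are also summarized by dose cohort and overall.

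The same numbers stand in all five synopses in the file (the initial protocol and Amendments 1 to 4). The file holds only synopses and schedules of events. The detailed escalation section is not included, and the content of Figure 1 (study schema) is not shown.

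**The concern.** In a 3 + 3 design a dose can be cleared on 3 subjects without a DLT. If such a dose became the HTD and exactly 12 subjects were added, the cohort would hold 15, not 18. The synopsis puts the range of 3 to 6, the fixed 12 and the fixed 18 close together and does not say that the selected dose must already have 6. A reader doing the sum could conclude that the plan gives two different sizes for its main cohort.

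That cohort is meant to supply the further safety, preliminary efficacy and immunogenicity data, and 18 is the only size given for it. If 15 were enrolled instead, every estimate at the recommended dose would be somewhat less precise, and an uncommon adverse event would be somewhat more likely to be missed.

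**Working it through.** **Inputs.** Escalation subjects at the selected dose, e: 3 to 6 if the escalation range is applied to that dose (Study Design). Expansion: 12. Stated total: 18. Ceiling: 30. Possible dose cohorts: 3, counting the de-escalation cohort.

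**Step 1: the stated total.** Total at the MTD/HTD = e + 12.

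| e | e + 12 |
|---|---|
| 3 | 15 |
| 4 | 16 |
| 5 | 17 |
| 6 | 18 |

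Strict 3 + 3 cohorts hold 3 or 6, so the practical alternatives are 15 and 18. The stated 18 is reproduced exactly with e = 6. Equivalently, the two fixed numbers give e = 18 − 12 = 6.

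**Step 2: the ceiling.** Two readings can be tested against 30.

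- *Reading A: a dose may be selected on 3 subjects, with no later filling.* At most two cohorts reach 6 before expansion, so the largest study is 6 + 6 + 12 = 24.
- *Reading B: the selected dose holds 6.* Cohort 1 may clear on 3, cohort 2 fail on 6, cohort 1 be filled to 6 and fail, and the de-escalation cohort fill to 6. The study is then 6 + 6 + 6 + 12 = 30. The smallest study with a selected dose is 3 + 6 + 12 = 21.

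Reading B reproduces both planned numbers. Reading A contradicts the 18 and gives no account of the 30. A maximum of 24 does not breach a ceiling of 30, so the ceiling itself is not in error under either reading.

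**Step 3: what 15 instead of 18 would cost.** The 10% event rate is an assumption for scale; the documents give none.

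| Quantity | Formula | n = 15 | n = 18 |
|---|---|---|---|
| Exact two-sided 95% upper limit, 0 events | 1 − 0.025^(1/n) | 21.8% | 18.5% |
| Chance of at least one event, true rate 10% | 1 − 0.9^n | 79.4% | 85.0% |

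The differences are 21.8 − 18.5 = 3.3 points and 85.0 − 79.4 = 5.6 points.

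**The case for a change.** The strongest case for a change is that an inferred condition is not a stated one. The expansion trigger names no minimum number treated, and the synopsis allows expansion at the HTD, so toxicity need not have forced a cohort up to 6. If a top dose could be accepted on 0 DLTs in 3, that outcome would be common: with an assumed true DLT rate of 10% its chance is 0.9³ = 72.9%, and with 20% it is 0.8³ = 51.2%. The route to 30 also needs a step the synopsis does not describe, namely returning to a cohort that cleared on 3 and filling it to 6. On this view the 15-subject outcome is the likely one, and one added clause would settle the matter.

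Part of this stands: no passage in the file states the 6-subject condition, and a short parenthesis showing 6 + 12 = 18 would be tidier. The rest does not carry. Those probabilities matter only if a dose may be selected on 3 subjects and the expansion then stops at 12. No passage says so, and the stated 18 argues against it. If the selected dose holds 6, the chance of a 15-subject cohort is zero. The range of 3 to 6 describes enrollment during escalation; it is not given as the number at the chosen dose. The rule for declaring a dose the MTD or HTD also belongs in the escalation section, so its absence from a synopsis does not show that the protocol lacks it.

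**Conclusion.** No change follows. The three numbers are consistent when read together: escalation cohorts hold 3 to 6, the selected one holds 6, and 12 more make 18. Followed as written, the plan enrolls 18 at the MTD/HTD. What remains is missing detail that study staff and analysts would fill from the stated total and the escalation rules.

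The size is small even on the unfavorable reading: at most 3 subjects, 3.3 points on the upper limit for zero events, and 5.6 points on the chance of seeing an event of 10% incidence. The synopsis attaches no hypothesis test, power statement, precision target or stopping rule to 18, and the planned safety analysis is descriptive, with denominators that will be whatever was enrolled.

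The conclusion rests on taking the twice-stated 18 as the intended size, which the 30 supports. It would need another look only if the full escalation section allowed a dose to be expanded from 3 subjects by exactly 12.

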# Enrollment (planned):

Up to 30 subjects will be enrolled in the study. In the dose escalation component, 3 to 6 subjects will be sequentially enrolled starting at cohort 1. In the dose expansion component (ie, once the MTD or HTD has been identified), an additional 12 subjects will be enrolled for a total of 18 subjects in the MTD/HTD cohort to obtain further safety, preliminary efficacy, and immunogenicity data.

# Diagnosis and Main Criteria for Inclusion:

Subjects must have histologically confirmed unresectable locally advanced or metastatic cancer that expresses HER2 (IHC 1+, 2+, or 3+). For malignancies other than breast and gastrointestinal, HER2 expression must be confirmed by a validated in situ hybridization (ISH) assay with results considered positive of HER2 amplification by ASCO/CAP HER2 testing guideline.

# Investigational Product, Dosage, and Mode of Administration:

ETBX-021 ( $5 \times 10^9$ ,  $5 \times 10^{10}$ , or  $5 \times 10^{11}$  VP in 1.0 mL) will be administered by SC injection every 3 weeks for 3 injections, followed by 3 booster injections at 3-month intervals.

# **Duration of Treatment:**

Subjects will receive treatment for up to 42 weeks (injections at 0, 3, and 6 weeks with booster injections at 18, 30, and 42 weeks) or until they experience progressive disease or unacceptable toxicity, withdraw consent, or if the Investigator feels it is no longer in their best interest to continue treatment.

# Reference Therapy, Dosage, and Mode of Administration:

Not applicable.

# Criteria for Evaluation:

**Safety:** Safety endpoints include assessments of DLT, MTD or HTD, treatment-emergent AEs, SAEs, and clinically significant changes in safety laboratory tests, physical examinations, ECGs, LVEF, and vital signs. Toxicities will be graded using the National Cancer Institute (NCI) Common Terminology Criteria for Adverse Events (CTCAE) Version 4.03.

**Efficacy:** Tumor response (ORR and DCR) will be evaluated according to RECIST Version 1.1; duration of response, PFS, and OS will also be evaluated.

**Exploratory Immune Analysis:** Immune responses will be detected and quantified in flow cytometrybased and serum assays.

**Exploratory Molecular Profiling, Analysis, and Rationale:** Genomic sequencing of tumor cells from tissue relative to non-tumor cells from whole blood will be profiled to identify the genomic variances that may contribute to response or disease progression and provide an understanding of molecular abnormalities. RNA sequencing will be conducted to provide expression data and give relevance to DNA mutations. Quantitative proteomics analysis will be conducted to determine the exact amounts of specific proteins and to confirm expression of genes that are correlative of response to vaccine immunotherapy and disease progression. All genomic, transcriptomic, and proteomic molecular analyses will be retrospective and exploratory.

#### **Statistical Methods:**

The rate of DLTs and the MTD or HTD will be assessed. Overall safety will be assessed by descriptive analyses using tabulated frequencies of AEs by grade using CTCAE Version 4.03 within dose cohorts and for the overall study population in terms of treatment-emergent AEs, SAEs, and clinically significant changes in safety laboratory tests, physical examinations, ECGs, LVEF, and vital signs. ORR and DCR will be evaluated according to RECIST Version 1.1 by dose cohort and overall; duration of response will also be evaluated. PFS and OS will be analyzed using Kaplan-Meier methods by dose cohort and overall.

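### The only MTD/HTD cohort mixes 6 dose-selection subjects with 12 expansion subjects, the DLT-rate denominator is unstated, and any toxicity rate that counts the six leans modestly low

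*Combined protocol and SAP*

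**What the plan says.** All references are to the Amendment 4 protocol synopsis.

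- **Primary Endpoints** lists DLTs with the MTD or HTD first. Primary Objectives includes the recommended phase 2 dose.
- **Study Design**: "the first part will involve dose escalation using a 3 + 3 design", and "In the first part, 3 to 6 subjects will be sequentially enrolled starting at dose cohort 1". The sentence on DLT assessment follows directly, beside the escalation part. Nothing comparable is said for the expansion part. Then: "Dose expansion will occur when the MTD or HTD has been determined".
- **Enrollment (planned)**: "an additional 12 subjects will be enrolled for a total of 18 subjects in the MTD/HTD cohort". The stated purposes are more safety information, early efficacy and immunogenicity.
- **Statistical Methods**: on the DLT rate, one sentence, "The rate of DLTs and the MTD or HTD will be assessed". It gives no analysis set, denominator, estimator or interval. The next sentence tabulates adverse events "within dose cohorts and for the overall study population", without separating escalation from expansion.

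The synopsis does not give the DLT count that lets a dose go forward. It names only the 3 + 3 design.

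**The concern.** The six escalation subjects at the MTD/HTD were used to decide that the dose was acceptable. Had they shown many DLTs, the dose would not have been expanded. Counting them again when estimating toxicity at that dose conditions on a favourable result, so the estimate leans low. Only the 12 expansion subjects are free of this selection, and no summary of them alone is planned.

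DLTs are a primary endpoint and bear on the recommended phase 2 dose. The error runs in the reassuring direction, and it grows in points as the true toxicity of the dose rises. An ordinary interval around the pooled rate does not reveal it.

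**Working it through.** **Inputs from the synopsis.** Expansion 12 and MTD/HTD total 18 (Enrollment); 3 to 6 escalation subjects per level, and three possible dose levels counting cohort -1 (Study Design); maximum enrollment 30 (Enrollment).

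**Inputs assumed.** The acceptance rule is at most 1 DLT in 6, the usual 3 + 3 convention. The true DLT rate p is taken over 10% to 40%. Neither is in the synopsis.

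**Step 1: reproduce the plan's counts.** 18 − 12 = 6 escalation subjects in the MTD/HTD cohort. Three levels × 6 + 12 = 30. Both agree with the stated figures, so six escalation subjects at the selected dose is the case to model.

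**Step 2: escalation subjects at an accepted dose.** Let X be the number of DLTs among the six. Given acceptance,

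E[X | X ≤ 1] = P(X=1) / P(X≤1) = 6p(1−p)^5 / [(1−p)^6 + 6p(1−p)^5] = 6p / (1 + 5p).

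The expected observed rate in the six is therefore p / (1 + 5p), which is below p for every p > 0. At p = 0.20 it is 0.20 / 2 = 10.0%.

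**Step 3: pooled rate over 18.** Expected rate = [6p/(1+5p) + 12p] / 18. At p = 0.20 this is (0.6 + 2.4) / 18 = 16.7%, a bias of −3.3 points. The expansion-only rate has expectation p.

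| True rate | P(dose accepted) | Six escalation subjects read | Pooled 18 reads | Bias (points) | Standard error, n=18 (points) |
|---|---|---|---|---|---|
| 10% | 88.6% | 6.7% | 8.9% | −1.1 | 7.1 |
| 20% | 65.5% | 10.0% | 16.7% | −3.3 | 9.4 |
| 30% | 42.0% | 12.0% | 24.0% | −6.0 | 10.8 |
| 40% | 23.3% | 13.3% | 31.1% | −8.9 | 11.5 |

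The standard error is √[p(1−p)/18].

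**Step 4: sensitivity to the rule.** Suppose a dose passes on 0/3, or on 1/3 followed by 0/3, and a 0/3 dose is then filled to six without re-applying the rule. The pooled rates are 9.1%, 17.3%, 25.2% and 33.0%. The bias is −0.9, −2.7, −4.8 and −7.0 points: same direction, somewhat smaller.

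**Step 5: total error.** With q = 6p/(1+5p), the pooled mean squared error is [q(1−q) + 12p(1−p)]/18² + bias². At p = 0.20, q = 0.6, and the root mean squared error is √[(0.24 + 1.92)/324 + 0.0333²] = 8.8 points. Expansion-only gives √(0.16/12) = 11.5 points. At 30% the pair is 11.0 and 13.2 points; at 40%, 13.1 and 14.1.

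**Step 6: precision of each figure.** With no events, the upper limit of the exact two-sided 95% interval is 1 − 0.025^(1/n): 26.5% for 0/12 and 18.5% for 0/18.

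**The case against.** The strongest reply has four parts.

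**The plan never says that the DLT rate is computed on the pooled 18.** A reader might infer it from the 18-subject cohort and the by-cohort tables. The documents do not go that far. The by-cohort phrase belongs to the adverse event sentence, the DLT sentence has no denominator, and DLT assessment is described only beside escalation. This stands. It does not remove the concern, because a rate from the six escalation subjects alone would be more biased (−10 points at a true 20%).

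**The at-most-one-DLT rule is convention, not text.** This also stands. The sizes above depend on it; the downward direction needs only that a dose is expanded because few DLTs were seen. A reader who lets a dose go forward on three subjects would find escalation rates near 5% (4.6%, 5.1% and 5.0% at true rates of 20%, 30% and 40%). That does not fit the stated 18, which implies six; with six the figures are 10% to 13%.

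**The bias is smaller than the sampling error, and the pooled estimate has the lower total error.** This is correct at every rate tabulated. It defeats the tempting conclusion that the recommended dose should rest on the 12 expansion subjects alone. It does not argue against showing both: an interval conveys sampling error, but nothing in a pooled table conveys selection.

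**The analysis is descriptive.** No test or threshold is attached to the pooled rate, so no formal decision rule is shown to be affected. This stands and limits the importance.

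The public text is at synopsis level. If a fuller protocol body defines the acceptance rule and the DLT-evaluable set, the sponsor can point to it.

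**Conclusion.** The point holds as a modest reporting weakness. The only MTD/HTD cohort defined combines 6 subjects used to select the dose with 12 who were not. The adverse event tables follow that cohort, and the denominator of the primary DLT rate is left open. Any DLT rate that includes the six is biased downward. Pooled over 18, the shortfall is about 1 to 6 points for true rates of 10% to 30%, and near 9 points at 40%, where the dose would be accepted only 23.3% of the time. Other adverse event rates share the bias to the extent that those events are related to DLTs.

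The sizes assume at most 1 DLT in 6 and exactly six escalation subjects at the dose; the first is not written in the synopsis. The documents do not support saying that the DLT rate is definitely taken from the pooled cohort, or that the pooled figure should be discarded.

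**What to change.** In Statistical Methods:

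1. State which subjects are DLT-evaluable and whether that includes the expansion part.
2. At the MTD/HTD, report treatment-emergent adverse events for the 12 expansion subjects beside the pooled 18. Do the same for the DLT rate if expansion subjects are DLT-evaluable. Give each rate an exact 95% confidence interval.
3. Label the pooled figure as including subjects used to select the dose.
4. Make both figures available to the recommended-phase-2-dose statement. Neither need replace the other.

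The cost is one extra table column and a wider interval for the expansion-only figure (Step 6 above). Dose, schedule and enrollment are unchanged.

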# Diagnosis and Main Criteria for Inclusion:

Subjects must have histologically confirmed unresectable locally advanced or metastatic breast cancer that expresses HER2 (IHC 1+ or 2+). Subjects with HER2 IHC 3+ tumors are excluded.

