# Diagnosis and Main Criteria for Inclusion:

Subjects must have histologically confirmed unresectable locally advanced or metastatic cancer that expresses HER2 (IHC 1+, 2+, or 3+).

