#### **Secondary Objectives:**

• Make preliminary assessments of objective response rate (ORR), disease control rate (DCR), duration of response, progression-free survival (PFS), and overall survival (OS) in subjects with HER2-expressing cancer treated with ETBX-021.

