## **Exploratory Objectives:**

• Evaluate the immunogenicity of ETBX-021 and determine the genomic and proteomic profile of subjects' tumors to identify gene mutations, gene amplifications, RNA-expression levels, and protein-expression levels. Correlations between genomic/proteomic profiles and efficacy outcomes will be assessed.

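### Should the efficacy summaries be split by tumor type and HER2 level now that eligibility reaches beyond HER2-low breast cancer?

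*Combined protocol and SAP*

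**What the plan says.** Through Amendment 2 the synopsis admitted only breast cancer with HER2 IHC 1+ or 2+. Under Diagnosis and Main Criteria for Inclusion it said: "Subjects with HER2 IHC 3+ tumors are excluded". Amendment 3 removed both the restriction to breast cancer and the IHC 3+ exclusion. Amendment 4 keeps the wider population and adds a condition for some tumor sites: "For malignancies other than breast and gastrointestinal, HER2 expression must be confirmed by a validated in situ hybridization (ISH) assay", with a result that counts as amplified.

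The efficacy sentences under Statistical Methods are the same in Amendments 2, 3 and 4. For response, "ORR and DCR will be evaluated according to RECIST Version 1.1 by dose cohort and overall"; for time-to-event endpoints, "PFS and OS will be analyzed using Kaplan-Meier methods by dose cohort and overall". No part of the Amendment 4 synopsis names a summary by tumor type or by the IHC level used for eligibility.

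Three other places bear on the point:

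- Secondary Objectives (Amendment 4) describes the efficacy aim as: "Make preliminary assessments of objective response rate (ORR), disease control rate (DCR), duration of response", together with PFS and OS, in subjects with HER2-expressing cancer, without division by site or level.
- Enrollment (Amendment 4) gives the purpose of the expansion: "for a total of 18 subjects in the MTD/HTD cohort to obtain further safety, preliminary efficacy, and immunogenicity data".
- Exploratory Objectives (Amendment 4) covers gene amplification and protein expression in the tumors, and states: "Correlations between genomic/proteomic profiles and efficacy outcomes will be assessed".

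**The concern.** The population changed in two respects, tumor site and HER2 level, while the efficacy summary stayed as it was for a breast-only, HER2-low trial. That looks like a section left behind by an amendment.

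With no control arm, a pooled response rate or Kaplan-Meier curve depends partly on who enrolled. Amendment 4 also applies a different HER2 entry standard outside breast and gastrointestinal tumors, so site and HER2 status are partly tied together by design. If cohorts were filled under different amendments, a difference between dose rows could also reflect case mix.

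At stake would be the reading of the preliminary efficacy results. Someone looking at the MTD/HTD row alone could not tell whether a few responses came from one tumor type or several.

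**Working it through.** **1. The plan's own numbers.** From Study Design and Enrollment (Amendment 4): three possible dose cohorts (1, 2 and, if needed, -1), up to 6 subjects each, plus 12 in expansion.

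- Maximum enrollment: 3 × 6 + 12 = 30, as stated.
- MTD/HTD cohort: 6 + 12 = 18, as stated.

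The synopsis gives no alpha, power, target ORR or reference rate, so there is no operating characteristic for case mix to disturb.

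**2. How far mix can move a pooled rate.** For two tumor groups with response rates p1 and p2 and share w in the first, pooled ORR = w·p1 + (1 − w)·p2. A change in share therefore moves it by (change in w) × (p1 − p2). The documents give no group-specific rates, so both the gaps and the change in share are assumptions. For a share moving from 0.2 to 0.8:

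| Assumed gap (points) | Shift = 0.6 × gap (points) |
|---|---|
| 0 | 0 |
| 10 | 6 |
| 20 | 12 |
| 30 | 18 |

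A second illustration assumes rates of 5% and 30% in 18 subjects, with the responder count binomial at the pooled rate:

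| Share in higher-rate group | Pooled ORR | Chance of 3 or more responders |
|---|---|---|
| 0% | 5.0% | 6% |
| 25% | 11.3% | 33% |
| 50% | 17.5% | 63% |
| 75% | 23.8% | 84% |
| 100% | 30.0% | 94% |

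The dependence on mix is real if the group rates differ. Nothing in the synopsis turns on reaching any of these values.

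**3. What subgroup rates would deliver.** Exact (Clopper-Pearson) 95% intervals:

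| Responders / n | Interval |
|---|---|
| 2/18 | 1.4% to 34.7% |
| 0/18 | 0 to 18.5% |
| 2/6 | 4.3% to 77.7% |
| 0/6 | 0 to 45.9% |
| 1/3 | 0.8% to 90.6% |
| 0/3 | 0 to 70.8% |

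Suppose the 18 split into three groups of 6 (an assumption) and two subjects respond. If both are in one group, its 2/6 interval overlaps the 0/6 intervals of the other two almost throughout.

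**4. Chance clustering.** If two responders fall at random among the 18, the probability that both are in the same group is:

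- groups of 6, 6 and 6: 3 × C(6,2) / C(18,2) = 45/153 = 29%;
- groups of 12, 4 and 2: (66 + 6 + 1)/153 = 73/153 = 48%.

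A table by tumor type would thus often show all of two responses in one group when there is no difference between groups.

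**5. Which conclusions depend on the breakdown.** Under Primary Objectives and Primary Endpoints (Amendment 4), the trial settles safety, DLTs, the MTD or HTD, and the recommended phase 2 dose. None of these is defined by ORR, DCR, PFS or OS. The secondary objective is worded for HER2-expressing cancer as one population, and the pooled summary answers it.

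**6. Whether the information would be lost.** HER2 expression is confirmed at screening (Time and Events Schedule), and histological confirmation of the cancer is an entry requirement. Both items are therefore known for every subject and can be listed beside dose, response and follow-up time. The synopsis does not mention listings; that silence does not exclude them.

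**The case for a change.** The best case for a change is that it costs little. One sentence and two small descriptive tables would use data already established at entry, add no subjects and involve no testing. Naming the groups in advance would limit later choice of a favorable one. The exploratory molecular correlations are not a substitute, because they are retrospective and do not tabulate outcomes by tumor type or by eligibility IHC level.

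Part of this stands. The synopsis names no such breakdown, and pooled rows may mix tumor types. They should not be read against a rate from a single tumor type.

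The rest is weaker:

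- It is not shown that every row is mixed. The documents do not say which cohort enrolled under which amendment; a cohort filled before Amendment 3 would be breast-only with no IHC 3+ tumors.
- HER2 level is partly covered. Amplification and protein expression are to be profiled and related to efficacy, although HER2 is not singled out there.
- A table by IHC level alone would still pool subjects admitted under different HER2 rules, because tumors outside breast and gastrointestinal sites also need ISH-confirmed amplification. Crossing the two factors would cut the groups further.
- Tables of ORR and DCR would leave PFS and OS untouched, and the subgroup rates would be too imprecise to interpret.

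**Conclusion.** No change to the plan is needed. Eligibility widened and the efficacy wording did not, but the summaries still answer the objective as written and no decision in the synopsis depends on the missing breakdown. The gap is one that analysts fill sensibly, by listing tumor type and HER2 status with each subject's dose, response, PFS and OS, and by describing pooled rows and curves as mixed-histology where they are. That is ordinary reporting practice.

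The size of any mix effect on a pooled ORR cannot be fixed from the documents. It runs from nothing to 18 points under the assumed gaps and the assumed 20% to 80% change in share. Formal subgroup rates would not resolve it: intervals for groups of six reach 46% for no responders and 78% for two.

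This rests on efficacy remaining preliminary and free of a benchmark or decision rule. It is also limited to the synopses and schedules on file; a fuller statistical section could already contain the breakdown.
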